	corticost_pre	Numeric (categorical)	0 = No	Corticosteroids (optional)
			1 = Yes	
			8 = Do not know	
	nsaid_pre	Numeric (categorical)	0 = No	NSAID (non-steroidal anti-
			1 = Yes	inflammatory drugs) (optional)
			8 = Do not know	
	ace_pre	Numeric (categorical)	0 = No	ACE inhibitor (angiotensin converting
			1 = Yes	enzyme inhibitors) (optional)
			8 = Do not know	
	arb_pre	Numeric (categorical)	0 = No	ARB (angiotensin II receptor blockers)
			1 = Yes	(optional)
			8 = Do not know	
	dmards_pre	Numeric (categorical)	0 = No	Biological disease-modifying anti-
			1 = Yes	rheumatic drugs (DMARDs) e.g. rituximab, tocilizumab, etc. (optional)
			8 = Do not know	
Section E	chemo_pre	Numeric (categorical)	0 = No	Chemotherapy (within 6 months or
Optional variables			1 = Yes	currently) for cancer (optional)
continued			8 = Do not know	
	gliclaz_pre	Numeric (categorical)	0 = No	Gliclazides (for diabetes or heart
			1 = Yes	failure) (optional)
			8 = Do not know	
	psychotrop_pre	Numeric (categorical)	0 = No	Psychotropic drugs (including
			1 = Yes	benzodiazepine, etc.) (optional)
			8 = Do not know	
	chloroq_pre	Numeric (categorical)	0 = No	Chloroquine (optional)
			1 = Yes	
			8 = Do not know	
	hydroxychloroq_pre	Numeric (categorical)	0 = No	Hydroxychloroquine (optional)
			1 = Yes	
			8 = Do not know	
	other1_pre_sp	Text		Other pre-symptomatic medication #1 (optional)
	other2_pre_sp	Text		Other pre-symptomatic medication #2 (optional)
	other3_pre_sp	Text		Other pre-symptomatic medication #3 (optional)
Section H	chills	Numeric (categorical)	0 = No	"Chills", or shivering (optional)
Symptoms at or prior to admission			1 = Yes	
(for SARI case			8 = Do not know	

	Variable	Туре	Values and coding	Definition
definition)	coryza	Numeric (categorical)	0 = No	Coryza (optional)
Optional variables			1 = Yes	
			8 = Do not know	
	vomit	Numeric (categorical)	0 = No	Vomiting (optional)
			1 = Yes	
			8 = Do not know	
	nausea	Numeric (categorical)	0 = No	Nausea (optional)
			1 = Yes	
			8 = Do not know	
	tach	Numeric (categorical)	0 = No	Tachypnoea or signs of low oxygen
			1 = Yes	saturation (optional)
			8 = Do not know	
	abdopain	Numeric (categorical)	0 = No	Abdominal pain (optional)
	·		1 = Yes	
			8 = Do not know	
	diarr	Numeric (categorical)	0 = No	Diarrhoea (optional)
			1 = Yes	
			8 = Do not know	
	palp	Numeric (categorical)	0 = No	Heart palpitations (optional)
Section H			1 = Yes	
Optional variables			8 = Do not know	
ontinued	chest	Numeric (categorical)	0 = No	Chest pain (optional)
			1 = Yes	
			8 = Do not know	
	dizzy	Numeric (categorical)	0 = No	Dizziness (optional)
			1 = Yes	
			8 = Do not know	
	dermato	Numeric (categorical)	0 = No	Rash or other dermatological
			1 = Yes	manifestation of COVID-19 (optional)
			8 = Do not know	
	confusion	Numeric (categorical)	0 = No	Confusion (optional)
			1 = Yes	
			8 = Do not know	
Section J	pcr2	Numeric (categorical)	0 = No	Whether a second PCR was done (if
Laboratory tests and results (SARS- CoV-2): during hospitalisation			1 = Yes	first PCR was negative) (optional)
			8 = Do not know	
	lab_covidpcr2	Numeric (categorical)	0 = Negative	Second PCR result for virus type
Optional variables			1 = Positive	SARS-COV-2 (optional)
			8 = Do not know	

Annex 2. Detailed pooled analysis plan

Pooled analysis outline

A pooled analysis is part of the primary objectives of the ECDC study. Country will be included potentially as a fixed effect or as a random effect in a multi-level model. Statistical heterogeneity between study sites will be determined, using the Q-test and the I^2 index [30].

Cases and controls will be described by baseline characteristics, and uni- and multivariable analyses performed as described in Section 3.13.1 for individual country level analysis.

Pooled analysis plan

Descriptive analysis

The proportion of eligible hospitalised cases and controls who agreed to participate in the study will be calculated. The proportion of patients not consenting will be documented. Patients excluded will be described in a study flowchart.

Patient inclusion depends on the SARI case definition(s) used for CVE and IVE estimates. Sensitivity analyses comparing CVE and IVE estimates based on alternative SARI case definitions are planned. In the primary analysis, CVE is estimated among SARI patients as defined in Section 3.5.2, while IVE is estimated among SARI patient defined as a hospitalised person with:

• at least one systemic symptom or sign: fever or feverishness, malaise, headache or myalgia or deterioration of general condition (asthenia or loss of weight or anorexia or confusion or dizziness);

AND

at least one respiratory symptom or sign (cough, sore throat or shortness of breath)

on admission or within 48 hours after admission. The symptoms should not have started (or clearly worsened, if chronic) more than seven days before swabbing.

Cases and controls will be described by baseline characteristics.

The main characteristics of each study will be summarised individually, and will include:

- Number of hospitals participating and catchment population;
- Beginning of vaccination campaigns for COVID-19 and for influenza vaccines;
 - Beginning of the study:
 - End of the study:
 - Vaccine product(s) used;
 - Estimated vaccine coverage in the country/region by vaccine brand, by target vaccine group;
- Number of patients screened:
- Number of patients excluded per reasons for exclusion.

Measure of effect

This study is a case—control study (test-negative design). The measure of association is an odds ratio (OR). This can be measured by logistic regression. An OR = 1 indicates no association between an exposure and the outcome. An OR > 1 indicates a potential risk factor, an OR < 1 indicates a potential protective factor, noting that the confidence interval around the OR helps with its interpretation.

For vaccination as preventive factor, the VE can be computed as VE = (1 - OR)*100. A 95% confidence interval is computed around the point estimate.

Pooled univariable analyses (VE estimates from crude OR)

Baseline characteristics of cases and controls will be compared using the chi-square test, Fisher's exact test, t-test or the Mann-Whitney test (depending on the nature of the variable and the sample size). The association (OR) between vaccination status and baseline characteristics will be measured for both case and control groups.

Stratified analysis

Depending on sample size, the analysis by vaccine product will be further stratified according to:

- sex:
- age group, e.g. 0–14 years, 15–49 years, 50–64 years, 65–79 years, 80+ years;
- specific chronic conditions (e.g. respiratory disease, diabetes, immunodeficiency⁹);
- absence, presence of at least one, presence of more than one high-risk condition;
- time: this will depend on timing of the pandemic/influenza season at sites/in countries and may just include one period at the start of the study once vaccines are available, and a specified period later on;
- dose (for CVE): partial vaccination, full vaccination, full vaccination plus booster;
- swab delay (0–3 days, 4–7 days; 8+ days);
- vaccination delay (<8 days, 8–14 days, >14 days, etc.);
- hospital admission delay (0-4 days, 5-9 days, 10 days +, onset after hospitalisation);
- previous vaccination against influenza and pneumococcal disease;
- prior infection with influenza or SARS-CoV-2 (prior to hospital admission for SARI);
- current co-infection with influenza (for CVE) or SARS-CoV-2 (for IVE) or other respiratory viruses (for both CVE and IVE);
- severity (ICU admission, ventilation/oxygen, death; for CVE);
- CVE/IVE at different time points in calendar time, e.g. by week or group of weeks (e.g. CVE for weeks 2–20, 21–42, etc.; IVE for interim season (to end January), and for the whole season);
- for the various groups of vaccines (if available/applicable), mode of injection (intradermal vs intramuscular);
- use of medications for chronic conditions (e.g. statins, for IVE);
- Other stratifications may be included.

Virus variant-specific outcomes will be used, if available and feasible at the time of analysis.

A sufficient sample size should be planned in order to ensure enough individuals in each stratum for a precise estimate. Effect modification will be assessed comparing the OR across the strata of the potential effect modifiers. Confounding will be assessed by comparing crude and adjusted OR for each potential confounder.

Multivariable analysis

A multivariable logistic regression analysis will be conducted to control for negative and positive confounding. Odds ratios and standard errors will be obtained. Variables will be tested for multicollinearity. Interactions will be tested using the likelihood ratio test or Wald's test and will be included in the model if significant at the 5% level. Factors other than statistical significance (prevalence of exposure, magnitude of OR) will also be used as criteria for inclusion of a variable or an interaction term. If possible, a variable for sex, age and onset time should always be included in the model.

Continuous variables

Continuous variables in the COVID-19/influenza datasets include age, time of onset of symptoms, and hospitalisations in the past 12 months. These variables can be coded as categories (e.g. age group, week of symptom onset, etc.) However, when coding continuous variables as categories, information may be lost, or introduce residual confounding and increase the standard error of the model. Tests will be carried out to see if these variables could be coded as a linear term, polynomial or a spline. In addition, a balance will be sought between simplicity of a model (so a non-expert can understand it), precision and a model that estimates the vaccine effect with the least bias.

Identifying heterogeneity, testing for heterogeneity

Country-specific crude and adjusted ORs and their confidence intervals will be plotted in separate forest plots. Following the core protocol minimises heterogeneity between studies. However, adherence to the protocol and study design and study quality characteristics will also be checked. Other study site characteristics will be assessed where feasible, such as types of circulating virus, information on healthcare use and organisation of the vaccination campaign. A qualitative decision will then be taken if one or more studies are substantially different from the other and should be excluded from the pooled analysis.

⁹ Note: Five common pre-existing conditions are currently used in pooled analyses: asthma, lung disease, heart disease, diabetes and immunodeficiency. This list may change over time, as it depends on which conditions all study sites are able to collect.

Statistical heterogeneity between studies will be tested using the Q-test and the I^2 index (see boxes for formulae below). The Q statistic follows a Chi² distribution (with k-1 degrees of freedom). The Q-test reports presence or absence of heterogeneity, while the I^2 index (based on the Q-statistic) quantifies the extent of the heterogeneity. According to the Higgins and Thompson classification, an I^2 index of around 25% indicates low, 50% indicates medium and 75% indicated high heterogeneity between studies.

$$Q = \sum w_i \left(\log(OR_i) - \log(OR_F) \right)^2$$

Where:

$$w_i = 1/v_i$$

 v_i is the inverse variance of the estimated log odds ratio of study i

$$\log(OR_F) = \frac{\sum w_i \times \log(OR_i)}{\sum w_i}$$

$$I^{2} = \frac{Q - (k - 1)}{Q} \times 100\%$$
 for $Q > (k - 1)$
 $I^{2} = 0$ for $Q \le (k - 1)$

Formulae are given here for completeness, in practice these measures are automatically calculated by many statistical software packages as part of the meta-analysis commands.

One-stage pooled analysis approach

If sample sizes are too small to measure vaccine effectiveness controlling for all potential confounders for each individual study site, a one-stage pooled approach will be used for analysis.

Individual study data will be pooled into one dataset and analysed as a one-stage model with study site as a fixed effect. This could provide a large enough sample size to obtain (for example) an estimate of CVE/IVE early in the study/season with reasonable precision. However, the results of this analysis should be interpreted with caution as it assumes not only that the underlying true exposure effect is the same in all studies, but also that the association of all covariates with the outcome is the same in all studies.

Formal tests of interaction between study site and covariates will be carried out to determine if the effect of each covariate differs across studies, to test the assumptions of the one-stage pooled fixed effect analysis.

The significance of interaction terms are themselves influenced by sample size and should also be interpreted with caution. Particular care needs to be taken if heterogeneity is found between study sites when using a one-stage fixed effects approach (see above section). Reasons for heterogeneity need to be thoroughly investigated and the assumptions underlying the one-stage pooling approach need to be revisited.

Controlling for hospital effect

Primary analysis will be carried out using simple logistic regression to obtain the individual study estimates. However, there could be an effect of the hospital that is related both to the exposure (propensity to vaccinate) and the outcome (in terms of swabbing behaviour). To adjust for this cluster effect, a multi-level logistic regression with each hospital as a random effect will be carried out when using one-stage pooled analysis.

Multi-level logistic regression can also be carried out for each individual study with hospital as a random effect. The two-stage model as outlined above will then be used to obtain a summary CVE/IVE measure, using these estimates.

The same applies to stratified analyses. The point estimates and confidence intervals from the multi-level and simple logistic regression will be compared in a sensitivity analysis.

Two-stage pooled analysis approach

If adequate sample size by study is achieved to obtain an adjusted OR, then a two-stage approach to pooled analysis will be taken.

Country-specific adjusted ORs and standard errors for the effect of COVID-19/influenza vaccination obtained from the individual studies will be combined in a model that incorporates random effects of the studies, to account for unmeasured country- and hospital-specific factors that differ between countries.

The country-specific exposure-disease effects (ORs) are then weighted by the inverse of their marginal variances. The marginal variance is the sum of the individual study-specific variances and the variance of the random study effects (τ 2). This will give the pooled odds ratio and standard error.

$$\log(OR_R) = \frac{\sum w_i^* \times \log(ORi)}{\sum w_i^*}$$
$$wi^* = \frac{1}{v_i + \tau^2}$$

The country-specific ORs and their confidence intervals, along with the pooled OR, will be presented graphically in a forest plot. This model will also be compared against a two-stage analysis with fixed study effects, to assess the effects of model assumptions.

If, despite the common protocol, covariates were not uniformly collected in the different studies, then an analysis will be carried out to exclude certain studies and a comparison made with the analysis, including all studies. In a different scenario, analyses can also be carried out excluding certain study participants for whom variables were collected differently.

Further analyses

Where sample size allows, further analyses will be carried out. These include:

- CVE/IVE by time since vaccination. Time since vaccination can be calculated by subtracting the date of
 vaccination from the date of onset. Time since vaccination can then be modelled as a continuous variable,
 including correction for either stable or increased rate of COVID-19/influenza over time; cumulative risk of
 COVID-19/influenza.
- CVE and IVE for patients with previous influenza vaccination (current influenza season) vs no previous influenza vaccination.
- IVE and CVE for patients with previous COVID-19 vaccination (within 6 months) versus no previous COVID-19 vaccination.
- If negative CVE is found in some target groups
 - assess possibility of vaccine-mediated enhanced disease (VMED), which could manifest as negative CVE, by comparing severity in vaccinated and unvaccinated patients. Results should show reduced severity among vaccinated patients; findings of increased severity in vaccinated patients could suggest VMED.
- As a sensitivity analysis, CVE/IVE will be calculated:
 - using WHO versus ECDC case definitions for SARI;
 - considering those vaccinated <X days before onset of symptoms as unvaccinated (in the main analysis these records will be excluded);
 - including SARI patients testing positive for influenza/SARS-CoV-2 in the control group;
 - including SARI patients testing positive for influenza/SARS-CoV-2 in the case group;
 - including SARI patients whose influenza/COVID-19 vaccine status is unknown in the control group;
 - using, as a control group, only SARI patients testing positive for at least one non-influenza respiratory virus/non-coronavirus;
 - considering different restrictions according to swabbing delay (e.g. <14 days, <10 days, etc.);
 - considering the sensitivity and specificity of PCR;
 - based on assumptions of previous infections;
 - excluding participants who received antivirals ≤14 days prior to swabbing;
 - excluding all participants with lab-confirmed influenza/SARS-CoV-2 at any time after symptom onset, to reduce bias.
- This can then be repeated using RSV as a sham outcome (if multiplex results are available for any sites).
 There should be no association between COVID-19/influenza vaccination and RSV-positivity in the absence of confounding.

Time can be input as a variable in the model to assess whether it can be an effect modifier.

Minimum sample size

Sample sizes may be very small for some sub-analyses. Different criteria can be used to determine whether the sample size is large enough to obtain a valid measure of VE;

- there are at least 10–15 cases (or controls, whichever is smaller) in the sub-analysis for crude analyses and more for adjusted analyses (e.g. at least 10 for each parameter in the model);
- there are ≥5 records in each cell of the two-by-two table of case and vaccination status;
- the precision of the estimate does not span both -200% and 90% (uninformative).

With low sample size, approaches include collapsing categories, or modelling continuous variables in a different way (if applicable). Sensitivity analyses can be carried out using penalised logistic regression.

Use of propensity scores

To limit the number of co-variables to include in the multivariable model, **if sample size allows**, estimates will be built and adjusted based on propensity scores. Propensity scores can be defined as the conditional probability of receiving the vaccine given a number of observed co-variables.

In propensity score matching, a propensity score for vaccination is calculated for cases and controls. Cases and controls are then matched by propensity score and all non-matched patients are discarded. Variables used to calculate the propensity score will include variables related to the vaccination and outcome. Care will be taken to avoid correlation and overmatching.

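### Annex 2 lets sites be dropped from the pooled analysis after their ORs have been plotted, does not confine the grounds to conduct or quality, and requires no all-site result alongside

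*Protocol*

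**What the plan says.** The Annex 2 subsection on identifying and testing for heterogeneity opens with the results: "Country-specific crude and adjusted ORs and their confidence intervals will be plotted in separate forest plots". It adds that "adherence to the protocol and study design and study quality characteristics will also be checked", and that other site characteristics, among them circulating virus, healthcare use and the organisation of the vaccination campaign, will be assessed where feasible. The next sentence concerns who stays in the pooled analysis: "A qualitative decision will then be taken if one or more studies are substantially different from the other and should be excluded". No criterion is given for what counts as different, and nothing keeps those who decide from using the ORs they have just seen.

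The test follows: "Statistical heterogeneity between studies will be tested using the Q-test and the I^2 index". Its reference is given as "The Q statistic follows a Chi² distribution (with k-1 degrees of freedom"), and k is not defined as all sites or as the sites kept.

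In the two-stage approach the country ORs "will be combined in a model that incorporates random effects of the studies"; a fixed-effects version serves as a comparison. A comparison with and without certain studies appears once, for covariates that were not uniformly collected: "then an analysis will be carried out to exclude certain studies and a comparison made with the analysis, including all studies". It is not extended to studies excluded as different.

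**The concern.** The chi-square reference for Q holds for all sites, or for a subset chosen independently of their ORs. If a site is removed because its OR stands out, the remaining sites have been selected to agree. A Q computed on them asks whether the agreeing sites agree, and the pooled interval understates how far VE varies between countries.

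Pooled VE is part of the primary objective (Section 2.1), so the estimate at stake is a main output. Two of the listed characteristics, circulating virus and campaign organisation, are also genuine reasons for VE to differ between countries. Excluding a country on those grounds removes the variation that the random-effects model is there to carry.

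**Working it through.** **A figure in the plan, to set the scale.** The protocol gives no power for Q. Table 5 fixes the precision of a single site. Its formula is n = 1.96² × [1/(p1(1−p1)) + 1/(p0(1−p0))] / [ln((OR+d)/OR)]², with p1 = OR·p0/(1−p0+OR·p0). For OR 0.3, vaccine coverage 0.5 and d = 0.2:
- p1 = 0.15/0.65 = 0.231
- the bracket is 5.63 + 4 = 9.63
- n = 3.84 × 9.63 / 0.261 = 141.8, against 142 in Table 5.

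The SE of that site's log OR is √(9.63/142) = 0.26.

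**Assumptions not in the documents.** 8 or 12 sites; 100 or 200 cases per site; mean VE 50%; between-site SD of log OR 0.3 or 0.4; 5% level for Q. Vaccine coverage of 50% and 1:1 controls are values that Table 5 uses. With OR 0.5 the bracket is 4.5 + 4 = 8.5, so the site SE is √(8.5/100) = 0.29 or √(8.5/200) = 0.21. An SD of 0.4 puts 95% of true site ORs within 0.5 × exp(±0.784), that is VE from −10% to 77%. An SD of 0.3 gives VE from 10% to 72%.

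**Method.** Site two-by-two tables were simulated from binomials (40,000 runs per setting, 0.5 added to each cell). Q and I² follow Annex 2, with v_i taken as the variance of the log OR. Annex 2 calls v_i the inverse variance, but w_i = 1/v_i is the usual weight only if v_i is the variance. Pooling is by DerSimonian–Laird random effects. Three analyses were compared: all sites; the site furthest from the pooled log OR in standard errors removed; one site removed regardless of its OR.

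| Setting (sites × cases, SD) | Q power: all sites | most deviant dropped | one dropped regardless of OR | Random-effects 95% CI coverage: all sites | most deviant dropped |
|---|---|---|---|---|---|
| 8 × 100, 0.4 | 0.65 | 0.28 | 0.60 | 0.92 | 0.80 |
| 8 × 200, 0.3 | 0.71 | 0.34 | 0.66 | 0.91 | 0.80 |
| 12 × 200, 0.3 | 0.84 | 0.56 | 0.81–0.82 | about 0.92 | 0.83 |

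In the first setting median I² falls from 0.60 to 0.32, from above the annex's medium benchmark (50%) towards its low one (25%). Coverage after a drop regardless of the OR stays at about 0.91 there.

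**No true heterogeneity.** With 8 sites of 142 cases, Q rejects about 5% of the time on all sites and 0.3% after the most deviant site is dropped. Chi-square on the remaining degrees of freedom is then the wrong reference.

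**A milder rule.** Suppose a site is dropped only when it lies more than 1.96 standard errors from the pool of the others (8 sites, 142 cases, OR 0.3, SD 0.3). Power still goes from 0.54 to 0.18 and coverage from 0.92 to 0.82.

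**Where it hardly matters for the test.** When power is near 1 (12 sites, 300 cases, SD 0.5), Q power goes only from 0.998 to 0.978.

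**What depends on k.** The power columns matter only if Q is run on the sites kept. The coverage columns do not depend on that, because they describe the pooled estimate itself.

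**The case against.** A reader might infer that the protocol tests heterogeneity only on the sites kept, that countries are removed because of their results, and that the loss of power is therefore built in. The text does not support that. The order of paragraphs suggests testing on the retained set but does not state it, and Section 3.13.3 speaks of heterogeneity between study sites without restriction. The exclusion sentence directly follows a list of adherence, design, quality and site characteristics, and it refers to studies that differ, not to results. Section 5.1.1 gives an innocent motive: Q has low power with few sites, so qualitative knowledge is used as well. Its examples are hospitals that can supply only cases or only controls. Exclusion on such grounds costs little, as the table shows.

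There are also safeguards. Country-level VE is itself a primary objective, so an excluded country's result remains an intended output. The central hub is to document and share its cleaning and analysis (Section 3.13.3), and in the one-stage approach reasons for heterogeneity are to be investigated.

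All of this stands, and it makes the effect conditional. It does not close the gap. The ORs are in view when the decision is taken, no wording separates a quality-driven exclusion from an OR-driven one, and no all-site pooled result is required beside it. Nor does running Q on all sites protect the pooled VE and its CI.

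**Conclusion.** The point holds as an open risk in the wording. Annex 2 permits exclusion from the pooled analysis that is influenced by the OR, and leaves unstated which sites enter Q and I².

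If the most deviant site is always dropped and Q is run on the rest, power falls from 0.65–0.84 to 0.28–0.56. Random-effects coverage falls from about 0.92 to 0.80–0.83 whichever sites Q uses. If exclusion is unrelated to the OR, the loss is close to nil. The true effect lies somewhere in that range and depends on how the decision is made in practice.

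The sizes rest on assumed numbers of sites, site sizes and between-site SDs, none of which the protocol gives. The documents do not show that any site will be removed because of its result.

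**What to change.** Amend the heterogeneity subsection of Annex 2 as follows:

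1. Exclusion from the pooled analysis rests only on pre-listed criteria of protocol adherence, design and data quality, judged without reference to the site's OR. Circulating virus and campaign differences are not grounds for exclusion.
2. Define k, and compute Q and I² on all eligible sites.
3. Always report the all-site pooled VE, Q and I² beside any estimate after exclusion.
4. Show any exclusion prompted by a site's OR only as a leave-one-out sensitivity analysis.

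Requiring the decision before any site OR exists would not be workable, because sites estimate their own VE and interim analyses recur. Judging on listed criteria without reference to the OR is enough.

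The cost is a rewritten subsection, an agreed list of criteria and a few extra lines of output; no further data are needed. The downside is that a flawed site noticed only through its OR stays in the all-site estimate and is dealt with in the sensitivity analysis.

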3.10 Sample size

Providing VE estimates for each separate study is one of the objectives of this project. Therefore, the minimum sample size should be estimated for each study to obtain precise CVE/IVE estimates. The pooled analyses should not prevent study teams at the country level from including a large enough sample size to obtain exact estimates for each country-specific study.

• Each study site/country to specify the minimum sample size calculation.

Sample size estimation in VE estimation is different from sample size estimation in hypothesis testing. Rather than focusing on whether a VE estimation includes 0% or not, it is the precision of the estimate which is more important. For example, with a VE of 70%, a lower boundary confidence interval of 1% does not provide a very informative VE estimate, even if the confidence interval does not include 0%. It is more important to have a VE estimate that is precise around the point estimate of 70% (e.g. with a lower boundary of 50%). In fact, a low VE estimate, which can be the case in particular stratified analyses, needs a very large sample size to provide a VE estimate where the confidence interval does not include 0%. For example, if the true VE is 5–10%, then a study providing a lower boundary not including 0% would be unreasonably large.

The following sample size estimates focus on precision of the VE estimate (Table 5).

The odds ratio (OR) has confidence intervals that are symmetrical around the point estimate in the log scale. However, due to the properties of the OR, these are asymmetrical around the point estimate on the arithmetic scale. The length of the confidence interval of an odds ratio on the arithmetic scale will therefore always be shorter at the lower limit (which will never reach zero). When converted to VE (VE=1-OR), the length of the confidence interval will always be shorter at the upper limit. Hence, the focus is on the precision of the lower limit of the confidence interval, and for Table 6 below, a potential range of between 10 and 30% (or 0.1–0.3) has been selected for this limit. A case-to-control ratio of 1:1 is also assumed, including varying vaccine coverage among the source population between 30% and 90%, and varying VE (with the OR between 0.1 and 0.7).

Table 5. Sample size calculations

Lower CI boundary	Controls/ case	Detectable OR	Vaccine coverage in source population/co ntrols	Number of cases	Number of controls	IVE/CVE	CI
0.3	1	0.1	0.3	60	60	90	60–98

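### Annex 2 defines v_i as an inverse variance while setting w_i = 1/v_i, so the printed formulae for Q and I² are wrong as written (minor)

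*Protocol*

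**What the plan says.** Annex 2, under Identifying heterogeneity, names the Q-test and the I² index as the statistical measures of between-study heterogeneity. It prints, in ordinary notation:

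- Q = Σ w_i (log OR_i − log OR_F)²
- w_i = 1/v_i, where v_i "is the inverse variance of the estimated log odds ratio of study i"
- log OR_F = Σ w_i log OR_i / Σ w_i
- I² = (Q − (k−1))/Q × 100% if Q > k−1, otherwise 0

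The reference distribution is given in the same section: "The Q statistic follows a Chi² distribution (with k-1 degrees of freedom". After the formulae the protocol adds: "Formulae are given here for completeness, in practice these measures are automatically calculated by many statistical software packages".

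The later section on the two-stage pooled analysis reuses the symbol in w_i* = 1/(v_i + τ²) and explains it in words: "The marginal variance is the sum of the individual study-specific variances and the variance of the random study effects".

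**The concern.** If v_i is an inverse variance, then 1/v_i is the variance itself. The noisiest site would carry the largest weight, both in Q and in the centring value OR_F, which is the reverse of what a heterogeneity statistic needs. A reader also meets two incompatible meanings of one symbol within the same annex.

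Q and I² are the only statistical heterogeneity measures that the protocol names (Section 3.13.3 and Annex 2). The one-stage section asks for particular care and a search for causes if heterogeneity is found, and Section 5.1.1 already warns that the test has little power with few sites. A version that can hardly ever signal would remove that prompt. This is a core protocol that other countries are encouraged to adopt, so its formulae may be copied into other protocols or scripts.

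**Working it through.** **Algebra.** Write Var_i for the variance of log OR_i. By the printed definition v_i = 1/Var_i, so w_i = 1/v_i = Var_i. The intended weight is 1/Var_i. The two differ by a factor Var_i², so a site with variance 0.1 enters Q with 0.01 times the intended weight.

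**Check against the stated chi-square distribution.** With fixed weights and no heterogeneity, the expected value of Q is Σ w_i Var_i − Σ w_i² Var_i / Σ w_i.

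- With w_i = 1/Var_i this is k − 1, as chi-square with k−1 degrees of freedom requires.
- With w_i = Var_i it is ΣVar_i² − ΣVar_i³/ΣVar_i, which depends on the scale of the variances and is not k − 1.

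**Check against the two-stage section.** There the denominator v_i + τ² is described as a sum of variances. Under the printed definition it would add an inverse variance to a variance, which has no meaning. Only v_i = Var_i fits.

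**Illustration.** The protocol states no Q, I², site odds ratios or standard errors, so there is no figure of its own to reproduce. The six sites below are assumed.

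| Site | OR | SE | log OR | Var | Share of weight, 1/Var | Share of weight, Var |
|---|---|---|---|---|---|---|
| 1 | 0.25 | 0.20 | −1.3863 | 0.0400 | 28.8% | 5.8% |
| 2 | 0.35 | 0.22 | −1.0498 | 0.0484 | 23.8% | 7.0% |
| 3 | 0.45 | 0.25 | −0.7985 | 0.0625 | 18.5% | 9.0% |
| 4 | 0.60 | 0.30 | −0.5108 | 0.0900 | 12.8% | 13.0% |
| 5 | 0.80 | 0.30 | −0.2231 | 0.0900 | 12.8% | 13.0% |
| 6 | 1.00 | 0.60 | 0 | 0.3600 | 3.2% | 52.1% |

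- Weights 1/Var: Σw = 86.66, log OR_F = −0.8917. Q = 6.11 + 0.52 + 0.14 + 1.61 + 4.97 + 2.21 = 15.56, p = 0.008 on 5 degrees of freedom. I² = (15.56 − 5)/15.56 = 68%.
- Weights Var, as printed: Σw = 0.6909, log OR_F = −0.3216. Q = 0.0453 + 0.0257 + 0.0142 + 0.0032 + 0.0009 + 0.0372 = 0.13, p > 0.99, I² = 0%.
- Expected Q with no heterogeneity under the printed weights: 0.1537 − 0.0485/0.6909 = 0.083, where chi-square needs 5.

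The collapse does not depend on which site has which standard error. The weighted sum of squares about its own weighted mean is at most the weighted sum about any other centre. Centred at the unweighted mean −0.6614, the squared deviations sum to 0.5255 + 0.1509 + 0.0188 + 0.0227 + 0.1921 + 0.4375 = 1.3475. No weight exceeds 0.36, so the printed Q cannot exceed 0.36 × 1.3475 = 0.49. That is far below k − 1 = 5, so I² is 0% in any ordering.

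**Second check at site sizes taken from Table 5.** Five sites were assumed with 77, 208, 289, 384 and 109 cases, control coverage 0.5 and as many controls as cases (Section 3.10: "A case-to-control ratio of 1:1 is also assumed"). Variances are the sum of reciprocal cell counts. This formula reproduces Table 5's lower limits at coverage 0.5: OR 0.5 with 289 cases gives 30.0%, OR 0.5 with 148 gives 20.0%, and OR 0.3 with 142 gives 50.0%. In 20,000 simulated sets around OR 0.5:

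- No heterogeneity: mean Q is 3.99 with correct weights (k − 1 = 4; 5.1% rejected at the 5% level) and 0.014 as printed (0% rejected).
- Between-site SD of log OR 0.5: 83% rejected with correct weights, 0% as printed.
- Between-site SD 1.0: 98% rejected with correct weights, 0% as printed. The printed I² was 0 in every set.

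**The case against.** The strongest reply is that nobody will compute Q this way. The annex says that the formulae are there for completeness and that packages do the calculation. Everything around the definition is standard: w_i = 1/v_i, the chi-square statement, the I² formula, and the wording of the two-stage section. A statistician would read v_i as the variance. This stands, and it limits the consequence. It does not make the definition true, and a formula printed for reference should be correct.

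A second reply is that the symbol may have been misread from the PDF: if the printed letter were w, the sentence would be right. This cannot be excluded from the text alone, but nothing shows it. The sentence is complete and legible, and it follows directly after w_i = 1/v_i, where v_i is the symbol that still needs a definition.

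Two stronger readings are tempting, and the documents support neither:

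- A reader might infer that the pooled vaccine effectiveness is shifted. OR_F here is the centring value inside Q. The pooled estimate comes either from one-stage logistic regression, which uses no w_i, or from the two-stage random-effects model, whose weights are correctly described in words. Two-stage fixed effects appear only as a comparison. In the six-site example OR_F does move, from 0.41 to 0.72, but that ordering pairs the largest standard error with the most extreme odds ratio. Over all 720 assignments of the same standard errors to the same odds ratios, it lies in the top 1.1% for shift, and the mean OR_F is 0.52 with correct weights against 0.53 as printed.
- A reader might infer that a decision rule would fail. No numerical threshold of Q or I² switches the model or excludes a site. Exclusion is a qualitative decision, and Section 5.1.1 asks for qualitative assessment as well.

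**Conclusion.** The definition of v_i is wrong as written and is inconsistent with two other statements in the same annex. That much follows from algebra alone. Applied literally, Q would shrink towards 0 and I² to 0% whenever log odds ratio variances are well below 1, as they are at the assumed site sizes (0.02 to 0.13 in the five-site check). The sizes quoted, Q 15.6 and I² 68% against Q 0.13 and I² 0%, rest on assumed site data and serve only as illustration. The practical effect is confined to hand-coded or copied implementations and to readers checking results against the annex. Severity is minor: most likely a drafting slip, with no demonstrated effect on the main pooled estimate.

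**What to change.** In Annex 2, under Identifying heterogeneity, delete the word inverse, so that v_i is defined as the variance of study i's estimated log odds ratio and w_i becomes the inverse variance. This also aligns the symbol with its use in w_i* = 1/(v_i + τ²). The cost is one word; no analysis decision, data item or software call changes. Any site or central script that codes Q or I² by hand should be checked once against a standard meta-analysis command.
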